1. PROTOCOL SYNOPSIS

Clinical Protocol: ESR-20-21010, UCCC-GI-21-01

Study Title: Durvalumab (MEDI4736) and Tremelimumab for Hepatocellular Carcinoma in Patients Listed for a Liver Transplant
Protocol Number: ESR-20-21010
Clinical Phase: II
Study Duration: Four years to complete accrual. Survival follow up will continue for 5 years.
Investigational Product(s) and Reference Therapy: 
 1. Durvalumab concentrate for solution for infusion will be supplied in glass vials containing 500 mg durvalumab at a concentration of 50 mg/mL. 2. Tremelimumab concentrate for solution for infusion will be supplied in glass vials containing 25 mg tremelimumab at a concentration of 20 mg/mL. 3. Locoregional therapy will be per institutional standards of care.
Research Hypothesis: Immunotherapy can safely downstage patients and achieve durable systemic disease control to improve clinical outcomes in HCC patients undergoing liver transplant.
Objectives: Primary Objectives: 
 1. To assess the safety of immunotherapy for treatment of HCC in patients listed for a liver transplant, with respect to cellular rejection rates. Secondary Objectives: 
 1. To assess the safety of immunotherapy for treatment of HCC in patients listed for a liver transplant, with respect to adverse events during treatment, and graft loss and mortality rates up to 30 days after transplant; 2. To assess the efficacy of immunotherapy for treatment of HCC in patients listed for a liver transplant, with respect to radiologic and pathologic responses, and survival outcomes. Exploratory Objectives: 
 1. To assess the correlation of peripheral blood immune cell profiles with clinical outcomes 2. To assess the correlation of baseline stool sample microbiome profiles with clinical outcomes
Study Design: ESR-20-21010 is a single-arm, open-label, Phase II, multicenter clinical trial designed to evaluate the safety and efficacy of durvalumab and tremelimumab for the treatment of hepatocellular carcinoma (HCC) patients who have cirrhosis or portal hypertension and are listed for a liver transplant. The key eligibility requirements include HCC, Child-Pugh score of up to 7, and ECOG PS of 0 or 1. Patients will be treated with the immunotherapy combination for up to 4 months. After a minimum 28 day gap following the final durvalumab dose, they will undergo locoregional therapy per institutional standards. Eventually, after a minimum 72-day gap from the end of immunotherapy, they will undergo liver transplant.

The primary endpoint is proportion of patients experiencing post-transplant rejection, graft loss, death, or loss to follow up (within 30 days of transplant). A total of 30 patients are to be enrolled, to allow at least 20 transplants for adequate primary endpoint analysis. An interim analysis after 10 patients will be performed to ensure safety. If there are untoward safety signals, study modification/discontinuation will be taken into consideration by the UCCC DSMB, investigators, the sponsor-investigator and AstraZeneca during the study and at interim analysis.

Number of Centers: 3

Number of Patients: 30

Study Population: HCC patients who have cirrhosis or portal hypertension and are listed for a liver transplant.

Inclusion Criteria:
 
 1. Hepatocellular carcinoma, diagnosed either by biopsy or by combination of cirrhosis and imaging criteria (contrast-enhanced CT or MRI) 2. Tumor confined to liver (no evidence of extrahepatic disease), with no macrovascular invasion 3. Patient evaluated by institutional Liver Transplant team and deemed eligible for transplant 4. Measurable disease by RECIST 1.1 5. No prior therapy for HCC 6. Adult patient (Age ≥ 18) 7. ECOG = 0 or 1 Child-Pugh Score = 5, 6, or 7 8. Creatinine < 1.5 ULN 9. Body weight > 30 kg

Exclusion Criteria:
 
 1. Extrahepatic disease 2. Variceal bleeding during 3 months prior to registration 3. Any other active cancer except: (a) Malignancy treated with curative intent and with no known active disease ≥ 5 years prior to the scheduled first dose of study treatment and of low potential risk for recurrence. (b) Adequately treated non-melanoma skin cancer or lentigo maligna without evidence of disease. (c) Adequately treated carcinoma in situ without evidence of disease. 4. Any other autoimmune disease deemed a risk in the setting of immunotherapy per treating physician's judgment 5. Any other illness or patient condition deemed a medical or logistical barrier for protocol therapy per treating physician's judgment

Investigational Products, Dose, and Mode of Administration:
 
Tremelimumab 300 mg via IV infusion x 1 dose on day 1, plus durvalumab 1500 mg via IV infusion Q4W starting on day 1, for up to a maximum of 4 months (5 doses of durvalumab). If a patient's weight falls to 30kg or below (≤ 30 kg), then the patient should receive weight-based dosing equivalent to 20 mg/kg of durvalumab Q4W after consultation between the investigator and study physician, until the weight improves to above 30 kg (> 30 kg), at which point the patient should start receiving the fixed dosing of durvalumab 1500 mg Q4W).

Other Treatments:

After a minimum of a 28-day gap following the final durvalamab dose, patients will undergo locoregional therapy to their tumor(s) per institutional standards. Eventually, after a minimum of a 72-day gap from the end of immunotherapy, they will undergo liver transplant.

Study Assessments and Criteria for Evaluation:

Safety Assessments:

During treatment, toxicities will be assessed per CTCAE v5 at each treatment visit. Laboratory evaluations will include complete blood counts, comprehensive metabolic panels, and thyroid function assessments. Symptoms will be evaluated using standard of care patient discussions. The primary endpoint is safety-based: patients with post-transplant “treatment failure”, defined as rejection, graft loss, death, or loss to follow up (within 30 days of transplant). This will be evaluated by at least weekly assessment of engrafted liver function tests.

Efficacy Assessments:

Radiologic response will be assessed after immunotherapy completion – prior to locoregional therapy initiation. Using both RECIST 1.1 and/or mRECIST. Pathologic response will be assessed in the explanted liver. Recurrence-free survival and overall survival will be assessed for five years.

[figure not shown]
Sample Size Determination, Statistical Methods and Data Analysis:

The primary endpoint of safety is a binary endpoint, and will be assessed in patients undergoing liver transplant. Historically, 10-20% of patients are expected to experience acute cellular rejection within 30 days of transplant. We propose that an observed proportion of 20% treatment failure will be a clear indicator of safety in this pilot study, whereas an observed proportion of 50% failure will be a clear indicator of failure. Using these guardrails, with at least 20 patients going to transplant, we will have 80.6% power to demonstrate a failure proportion of 20% (4 patients experiencing failure) versus a null of 50% (10 patients experiencing failure), with a one-sided alpha of 0.05. With 25 patients going to transplant, the power will increase to 86% (other parameters being the same).

For the secondary endpoint of death-censored graft loss, within 30 days of transplant 2.5% of patients undergoing a liver transplant in these settings experience graft loss. If $\geq 7.5\%$ of patients in this study experience graft loss within 30 days of transplant, it will be considered a serious safety signal.

For the efficacy endpoints, radiologic and pathologic response rates will be assessed as proportions, and overall and recurrence-free survival will be assessed using the Kaplan Meier method.

2. SCHEMA

3. STUDY CALENDAR

Milestone	Screening	I/O		Post I/O Eval ^l	LR Therapy ^m	Transplant ⁿ	Post-op	Long Term Follow-up
Timing		D1	Q4W	28 days post I/O	28 days post I/O minimum	72 days post I/O minimum	Q7 days for 30 days	Q3 mo for 1 st yr then q6 mo up to 5 yrs
Window	-28 days		+/- 3 days	+/- 3 days			+/- 1 day	+/- 4 weeks
Durvalumab ^a		X	X					
Tremelimumab ^b		X						
LR Therapy ^c					X			
Transplant						X		
Consent ^d	X							
Demographics	X							
Medical Hx	X						X ^t	
Con Meds	X							
Physical Exam ^e	X	X	X	X			X ^t	
Vital Signs	X	X	X	X		X		
Height	X							
Weight	X	X	X	X		X		
Child-Pugh	X							
ECOG PS	X	X	X	X	X			
AE/SAEs		X	X	X	X			
CBC w/diff	X	X	X	X	X	X	X	X
CMP	X	X	X	X	X	X	X	X
TSH, amylase, lipase ^f	X		X	X				
INR	X		X	X	X	X	X	
AFP	X			X	X	X		X
βhCG ^g	X							
CT Chest ^h	X			X				
MRI Liver ⁱ	X			X				X ^o
Bone scan (if clinically indicated)	X							
Tumor Assessments ^r	X			X				
Survival Data ^q					X	X	X	X
Rejection Data							X	X ^p
Correlative Blood collection ^j	X ^j			X ^j		X ^j	X ^j	
Stool collection ^k	X							
Tissue collection ^l						X ^l		

I/O: Immunotherapy; LR: Locoregional; CBC: Complete blood count; CMP: Comprehensive metabolic panel (sodium, potassium, chloride, bicarbonate, urea, creatinine, calcium, protein, albumin, AST, ALT, alkaline phosphatase, bilirubin)

a. Up to 5 treatments

b. Tremelimumab is only administered one time on Day 1 of the first cycle – only 1 dose for the entire study. It is not given on the first day of every subsequent cycle.

- c. Per treating physician discretion – TACE, SIRT, etc.
- d. Every effort should be made to minimize the time between consent and starting treatment
- e. Physical exam will be directed toward key symptoms, signs, and safety evaluations, per treating physician's discretion
- f. If TSH is abnormal, then free T3 and/or free T4 should be checked
- g. For women of childbearing potential only. Serum pregnancy test performed within 7 days prior to the first dose of trial treatment. A urine test may be considered if serum test is not appropriate.
- h. With or without contrast, per treating physician discretion
- i. With contrast
- j. Correlative blood samples may be collected with other SOC labs include the following. See Correlative section #9 for more information and the Laboratory Manual.
 - Two 10 mL EDTA tubes which must be collected after eligibility is confirmed but prior to I/O..
 - Two 10 mL EDTA tubes collected at the post I/O evaluation timepoint.
 - Two 10 mL EDTA tubes collected 4 weeks post-transplant +/- 3 days.
- k. Per correlative section #9. Stool sample must be collected after eligibility is confirmed but prior to I/O.
- l. tissue will be sequenced by CARIS as a SOC process.
- m. The post-I/O safety eval must occur 28 days following the final dose of durvalumab.
- n. A minimum 28-day gap after I/O before beginning L/R is required. L/R therapy can continue/repeat per treating physician discretion.
- o. At least after 72 days following final dose of durvalumab.
- p. Every 6 months +/- 1 month for standard of care, survival and disease progression data may be abstracted from this imaging.
- q. Transplant graft rejection data will be collected at 30 days after transplant and at 3 months and 6 months during long term follow-up.
- r. Subjects should be contacted by telephone or seen in clinic every 3 months from the end of I/O for the first year then every 6 months for up to 5 years to assess for survival status. Time-points noted under L/R Therapy, Transplant, and Post-op are intended to indicate that depending on the timing of each these may contain q3month time-points from I/O at which this data collection should occur.
- s. Tumor assessments must include measures for either RECIST 1.1 or mRECIST or both if institutionally allowed.
- t. 30-day post-transplant SOC visit in oncology with a +/- 7 day window to include medical history and physical.

Table of Contents

1.	Protocol Synopsis	2
2.	SCHEMA 5	
3.	STUDY CALENDAR	6
4.	abbreviations and definition of terms	10
5.	OBJECTIVES 14	
5.1.	Primary Objectives.....	14
5.2.	Secondary Objectives.....	14
5.3.	Exploratory Objectives	14
6.	BACKGROUND	14
6.1.	Immunotherapy Background	14
6.2.	Durvalumab (MEDI4736) Background	15
6.3.	Tremelimumab Background	16
6.4.	Durvalumab in combination with tremelimumab	16
6.5.	Durvalumab + tremelimumab combination therapy dose rationale.....	17
6.6.	Hepatocellular Carcinoma Background.....	18
6.7.	Correlative Studies Background	19
7.	PATIENT SELECTION: Eligibility.....	20
7.1.	Inclusion Criteria	20
7.2.	Exclusion Criteria	21
7.3.	Inclusion of Women and Minorities	23
8.	REGISTRATION PROCEDURES	23
8.1.	Assignment of Screening and Subject Numbers.....	23
8.2.	Patient Screening	24
8.3.	Patient Registration.....	24
8.4.	General Guidelines.....	24
9.	BIOMARKER, CORRELATIVE, AND SPECIAL STUDIES	25
9.1.	Biomarker Plan	25
9.2.	Exploratory/Ancillary Correlative Studies	27
10.	TREATMENT PLAN.....	28

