7. PATIENT SELECTION: ELIGIBILITY

7.1. Inclusion Criteria

1. Hepatocellular carcinoma, diagnosed either by biopsy or by combination of cirrhosis and imaging criteria (contrast-enhanced CT or MRI).
2. Tumor confined to liver with no vascular invasion and no evidence of extrahepatic disease.
3. Patient evaluated by institutional Liver Transplant team and deemed eligible for transplant.
4. At least 1 lesion, not previously irradiated, that qualifies as a RECIST 1.1 target lesion (TL) at baseline. Tumor assessment by computed tomography (CT) scan or magnetic resonance imaging (MRI) must be performed within 28 days prior to randomization.
5. No prior therapy for HCC at any time.
6. Age ≥18 years at the time of study entry.
7. ECOG score of 0 or 1

8. Child-Pugh Score of 5, 6, or 7
9. Body weight >30 kg
10. Patients must have adequate organ and marrow function as defined below:

Hemoglobin	≥9.0 g/dL
Absolute neutrophil count	≥1.0 × 10 ⁹ /L
Platelet count	≥50 × 10 ⁹ /L
Serum bilirubin*	≤3 mg/dL
AST(SGOT)/ALT(SGPT)	≤2.5 x institutional upper limit of normal unless liver metastases are present, in which case it must be ≤5x ULN
Creatinine	< 1.5 ULN
Measured creatinine clearance	>40 mL/min
OR	
Calculated creatinine clearance (CL)	
CL>40 mL/min by the Cockcroft-Gault formula (Cockcroft and Gault 1976) or by 24-hour urine collection for determination of creatinine clearance:
 
Males: Creatinine CL = $\frac{\text{Weight (kg)} \times (140 - \text{Age})}{72 \times \text{serum creatinine (mg/dL)}}$ (mL/min)
 
Females: Creatinine CL = $\frac{\text{Weight (kg)} \times (140 - \text{Age})}{72 \times \text{serum creatinine (mg/dL)}} \times 0.85$ (mL/min)

11. Capable of giving signed informed consent which includes compliance with the requirements and restrictions listed in the informed consent form (ICF) and in this protocol.
12. Patient is willing and able to comply with the protocol for the duration of the study including undergoing treatment and scheduled visits and examinations including follow up.

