14.3.1. Evaluation of Response

Radiologic response will be assessed after immunotherapy completion – prior to locoregional therapy initiation using RECIST 1.1 and/or mRECIST. Pathologic response will be assessed in the explanted liver. Recurrence-free survival and overall survival will be assessed for five years.

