16. MEASUREMENT OF EFFECT

16.1. **Antitumor Effect – Solid Tumors**

For the purposes of this study, patients should be re-evaluated for response 28 days after

completion of I/O +/-3 days. . In addition to a baseline scan, confirmatory scans should also be obtained (not less than 4) weeks following initial documentation of objective response.

Response and progression will be evaluated in this study using RECIST version 1.1 and/or the mRECIST guidelines (both when institutionally allowed).

Definitions

Evaluable for Toxicity. All patients will be evaluable for toxicity from the time of their first treatment with *Durvalumab*

Evaluable for Response. All patients who have received at least one cycle of therapy and have their disease re-evaluated will be considered evaluable for response (exceptions will be those who exhibit objective disease progression prior to the end of Cycle 1 who will also be considered evaluable). Patients on therapy for at least this period and who meet the other listed criteria will have their response classified according to the definitions set out below.

Evaluable Non-Target Disease Response. Patients who have lesions present at baseline that are evaluable but do not meet the definitions of measurable disease, have received at least one cycle of therapy, and have had their disease re-evaluated will be considered evaluable for non-target disease. The response assessment is based on the presence, absence, or unequivocal progression of the lesions.

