16.1.3.2. Evaluation of Non-Target Lesions

Complete Response (CR): Disappearance of all non-target lesions and normalization of tumor marker level. All lymph nodes must be non-pathological in size (<10 mm [<1 cm] short axis).

Note: If tumor markers are initially above the upper normal limit, they must normalize for a patient to be considered in complete clinical response.

Non-CR/Non-PD: Persistence of one or more non-target lesion(s) and/or maintenance of tumor marker level above the normal limits.

Progressive Disease (PD): Appearance of one or more new lesions and/or *unequivocal progression* of existing non-target lesions. *Unequivocal progression* should not normally trump target lesion status. It must be representative of overall disease status change, not a single lesion increase.

Although a clear progression of “non-target” lesions only is exceptional, the opinion of the treating physician should prevail in such circumstances, and the progression status should be confirmed at a later time by the UC Principal Investigator.

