16.1.3.3. Evaluation of Best Overall Response

The best overall response is the best response recorded from the start of the treatment until disease

progression/recurrence (taking as reference for progressive disease the smallest measurements recorded since the treatment started). The patient's best response assignment will depend on the achievement of both measurement and confirmation criteria.

Integration of target, non-target, and new lesions into response assessment

Target Lesions	Non-Target Lesions	New Lesions	Overall Response	Best Response for This Category Also Requires
Target lesions ± non target lesions				
CR	CR	No	CR	Normalization of tumor markers, tumor nodes <10 mm & confirmation ≥ 4 wks.
CR	Non-CR/non-PD	No	PR	Normalization of tumor markers, tumor nodes <10 mm & confirmation ≥ 4 wks.
CR	Not all evaluated	No	PR	confirmation ≥ 4 wks
PR	Non-PD/not all evaluated	No	PR	confirmation ≥ 4 wks
SD	Non-PD/not all evaluated	No	SD	Documented at least once ≥4 weeks from baseline
Not all evaluated	Non-PD	No	NE	
PD	Any	Any	PD	no prior SD, PR or CR
Any	PD	Any	PD	no prior SD, PR or CR
Any	Any	Yes	PD	no prior SD, PR or CR
Non target lesions ONLY				
No Target	CR	No	CR	Normalization of tumor markers, tumor nodes <10 mm
No Target	Non-CR/non-PD	No	Non-CR/non-PD	
No Target	Not all evaluated	No	NE	
No Target	Unequivocal PD	Any	PD	
No Target	Any	Yes*	PD	

Note: Patients with a global deterioration of health status requiring discontinuation of treatment without objective evidence of disease progression at that time should be reported as "symptomatic deterioration." This is a reason for stopping therapy, but is NOT objective PD. Every effort should be made to document the objective progression even after discontinuation of treatment.
 
*Investigators should record all new lesions. If the new lesion is felt to be equivocal, treatment may be continued pending further assessments.
				

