16.2. Other Response Parameters: mRECIST

The modified Response Evaluation Criteria in Solid Tumors (mRECIST) was developed in 2008 by the American Association for the Study of Liver Disease (AASLD) as an amended version of the RECIST, a method of measuring tumor response to treatment. mRECIST was developed specifically for HCC.

Contrast-enhanced CT or MRI is the imaging modality of choice for evaluating lesions. European Association for the Study of the Liver (EASL) guidelines recommend evaluating for mRECIST criteria 1 month after undergoing treatment (surgery, locoregional therapy or initiation of systemic chemotherapy). mRECIST) This may be used in liver lesions meeting the following criteria:

- Can be accurately measured in at least one dimension as 10 mm or more (measure longest diameter).
- Suitable for repeat measurement.
- Intratumoral arterial enhancement on contrast-enhanced CT or MRI.

Target Lesion Responses are defined as the following (RECIST 1.1 is listed for comparison):

	RECIST 1.1	mRECIST
Complete response	Disappearance of all target lesions	Disappearance of any intratumoral arterial enhancement in all target lesions
Partial response	At least a 30% decrease in the sum of diameters of target	At least a 30% decrease in the sum of diameters of

	lesions, taking as reference the baseline sum of the diameters of target lesions	viable (enhancement in the arterial phase) target lesions, taking as reference the baseline sum of the diameters of target lesions
Stable disease	Any cases that do not qualify for either partial response or progressive disease	Any cases that do not qualify for either partial response or progressive disease
Progressive disease	An increase of at least 20% in the sum of the diameters of target lesions, taking as reference the smallest sum of the diameters of target lesions recorded since treatment started	An increase of at least 20% in the sum of the diameters of viable (enhancing) target lesions, taking as reference the smallest sum of the diameters of viable (enhancing) target lesions recorded since treatment started

Non-Target Lesion Responses are defined as the following (RECIST 1.1 is listed for comparison)

	RECIST 1.1	mRECIST
Complete response	Disappearance of all non-target lesions	Disappearance of any intra-tumoral arterial enhancement in all non-target lesions

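### No single criterion defines a radiologic responder: each centre may read RECIST 1.1, mRECIST or both, so there may be no criterion read in every patient

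*Combined protocol and SAP*

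**What the plan says.** Four places deal with the response criterion, and none settles it.

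- Study Calendar, footnote s: "Tumor assessments must include measures for either RECIST 1.1 or mRECIST or both if institutionally allowed".
- Section 14.3.1 places the assessment after immunotherapy and "prior to locoregional therapy initiation using RECIST 1.1 and/or mRECIST".
- Section 16.1 also uses and/or, asking for both where the institution allows it.
- The synopsis asks for both and, in the same phrase, says and/or.

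Section 14.3 plans radiologic and pathologic response as proportions. It names no criterion, no rule for patients in whom the two readings disagree, and no split by criterion.

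Inclusion criterion 4 in section 7.1 requires "At least 1 lesion, not previously irradiated, that qualifies as a RECIST 1.1 target lesion (TL) at baseline". The Study Calendar and section 11.8 schedule a contrast liver MRI at baseline and at the evaluation 28 days after immunotherapy. The synopsis gives 3 centres and 30 patients.

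**The concern.** RECIST 1.1 measures the whole lesion. mRECIST measures the part that still enhances in the arterial phase. The footnote is a data-collection rule, and a centre that follows it exactly may record only one of the two. If one centre records only RECIST 1.1 and another only mRECIST, neither criterion is available in every patient, and the gap may not be recoverable at analysis without re-reading scans. The response rate could then reflect the mix of instruments across centres as well as the effect of the drugs. The trial is open-label with a single arm, so a responder definition chosen after the readings are in would be a post hoc choice. Radiologic response is part of the second secondary objective.

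**Working it through.** **No figure to reproduce.** The documents give no target, null value, power or precision for the response rate. The check is a comparison of definitions followed by an illustration on assumed rates.

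**Step 1: can the criteria disagree?** For target lesions, let B be the baseline sum of diameters, W the whole-lesion sum after immunotherapy, and V the enhancing (viable) sum after immunotherapy.

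- RECIST 1.1 (section 16.1.3.1): complete response needs the target lesions to disappear; partial response needs (W − B)/B ≤ −30%.
- mRECIST (section 16.2): complete response is "Disappearance of any intratumoral arterial enhancement in all target lesions"; partial response needs (V − B)/B ≤ −30%, with the baseline sum of target-lesion diameters as the printed reference.

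Two illustrative lesions with B = 50 mm:

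- W = 50, V = 30. RECIST 1.1: (50 − 50)/50 = 0%, stable disease. mRECIST: (30 − 50)/50 = −40%, partial response.
- W = 45, V = 0. RECIST 1.1: (45 − 50)/50 = −10%, stable disease. mRECIST: complete response.

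**Step 2: in which direction?** V cannot exceed W. So W ≤ 0.7B implies V ≤ 0.7B, while the first lesion shows that the converse fails. For the same target lesions, under the printed definitions, reading mRECIST can only hold or raise the proportion that meets the partial-response threshold.

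**Step 3: how large?** The documents do not say. Assume three equal centres, k of them reading only mRECIST, readings combined into one proportion, and true rates pR (RECIST 1.1) and pM (mRECIST):

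expected rate = (1 − k/3) × pR + (k/3) × pM

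| Assumed pR, pM | k = 0 | k = 1 | k = 2 | k = 3 |
|---|---|---|---|---|
| 15%, 25% | 15.0% | 18.3% | 21.7% | 25.0% |
| 20%, 35% | 20.0% | 25.0% | 30.0% | 35.0% |
| 20%, 50% | 20.0% | 30.0% | 40.0% | 50.0% |

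For example, with 20% and 35% and k = 1: (2/3) × 20 + (1/3) × 35 = 25.0%. For scale, exact 95% intervals at 30 patients are 7.7% to 38.6% for 6 responders and 14.7% to 49.4% for 9. Most of these shifts are smaller than the sampling uncertainty, but they are systematic and the interval does not account for them. The denominator may also be below 30, because section 16.1 restricts response to evaluable patients.

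**Step 4: is one criterion available to all?** Inclusion criterion 4 guarantees a RECIST 1.1 target lesion in every patient. mRECIST needs arterial enhancement in the lesion (section 16.2), which section 7.1 does not require of the target lesion. No section requires a RECIST 1.1 reading in every patient after immunotherapy.

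**Secondary check: the best-response table.** Section 16.1.3.2 defines Non-CR/Non-PD as "Persistence of one or more non-target lesion(s) and/or maintenance of tumor marker level above the normal limits". In section 16.1.3.3, target CR with non-target Non-CR/non-PD is PR, with the added requirement "Normalization of tumor markers, tumor nodes <10 mm & confirmation ≥ 4 wks". Read literally, a patient whose target lesions disappear but whose marker stays raised enters that row and cannot satisfy it. The row for target PR asks only for confirmation.

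**The case against.** The strongest reply is that the plan leans towards RECIST 1.1. It is the entry criterion, section 16.1 sets out its rules in full, mRECIST appears under other response parameters, and section 16.1 asks for both where allowed. Section 17.3 also says investigators will settle all measurements before the first patient is enrolled. This makes drift between centres less likely, but it does not override a footnote that accepts either instrument alone.

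A reader might infer that the plan pools the two readings, or counts a response by either. It says neither. Section 14.3 speaks of proportions without saying how they are formed, so the supportable statement is that the criterion is unspecified.

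It is also fair to say that the rates and centre mix in the illustration are assumed, that no document shows any centre reading only mRECIST, and that no benchmark or decision rests on the rate. An argument that comparison with published rates is lost has no basis in the plan, which specifies no such comparison.

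The choice of headline criterion is partly preference: section 16.2 describes mRECIST as developed for HCC. That stands. The need is for one criterion, named in advance.

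On the table, a reader might infer that the plan reverses the order of benefit by denying PR to the deepest responders. That rests on one cell that repeats the complete-response row word for word and may be a merged or misplaced cell. Sections 16.1.2 and 16.1.3.2 tie marker normalisation to complete response, and disappearance of target lesions also satisfies the 30% decrease for PR. The row needs checking and supports no stronger claim.

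**Conclusion.** The concern holds for the responder definition. As written, the documents allow a trial in which neither criterion is read in every patient, and they do not say which one defines a responder. The definitions alone show that the same lesion can be classified differently, and that more mRECIST reading can only hold or raise the share of patients meeting the target-lesion threshold. The size cannot be derived from the documents. On the assumed rates above, moving from no centre to all three on mRECIST shifts the rate by 10 to 30 points, and this requires that readings be combined, which the plan does not state.

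The point affects a secondary efficacy endpoint. The primary safety endpoint and the sample size do not depend on it. The best-response row is a separate, minor matter to reconcile; the documents give no count of patients it could affect.

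**What to change.** In footnote s, section 14.3.1, section 16.1 and the synopsis:

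- require RECIST 1.1 measurements in every patient at baseline and at the scan after immunotherapy;
- name one criterion in advance as the responder definition for all centres (RECIST 1.1 is the one that eligibility guarantees will apply to everyone);
- report mRECIST as a separate proportion among patients with a baseline mRECIST reading;
- state that the two are never combined and that a response by either is not counted.

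In section 16.1.3.3, check the source table. If the row giving PR for target CR with Non-CR/non-PD does require normalised markers, reconcile it with section 16.1.3.2.

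These edits concern endpoint scoring only. The cost is protocol and SAP wording. Whole-lesion diameters come from the contrast MRI already scheduled, so no scan is added. A centre that reads only mRECIST must also record those diameters, and the headline rate may be lower if RECIST 1.1 is chosen.
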